8.12. Number of Trial Subjects

[REDACTED]

[REDACTED]

[REDACTED]

STATISTICAL CONSIDERATIONS

9.5. Description of the Statistical Design

Since the trial is to inform product development, no statistical design is required.

9.6. Sample Size

A minimum of 30 participants will be utilised for each investigation. According to the FDA guidance on Human Factors Engineering, a sample size of 30 will allow a mean of 99% of usability problems to be identified (minimum of 97%). This is deemed to be appropriate for this investigation as the product is in feasibility, and the intent is to assess the usability of the user interface to determine further design iterations.

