7.2. Objectives

[figure not shown]
Primary objective:

- To evaluate the performance, comfort and ease of use of the [REDACTED] mask [REDACTED] in a home environment in regards to the participants' view of overall comfort, experience and satisfaction.
- [REDACTED]
- [REDACTED]

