7.3. Population

Approximately 60-70 participants will be recruited for the trial by NTLSC.

After identification, the co-ordinating investigator or contact persons from the institutions (or those identified by delegation log) will contact potential participants and obtain informed consent from the subjects to be enrolled.

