9.7. Pass/Fail Criteria

There is no pass/fail criteria for this trial as the primary objective of the trial is to gain feedback.

[REDACTED]	[REDACTED]
[REDACTED]	[REDACTED]

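### Does section 9.6 overstate what 30 participants can reveal when it says they identify a mean of 99% of usability problems?

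*Combined protocol and SAP*

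**What the plan says.** Section 9.6 (Sample Size) sets a floor: "A minimum of 30 participants will be utilised for each investigation". It takes the supporting figure from a cited source, "According to the FDA guidance on Human Factors Engineering", and reports that "a sample size of 30 will allow a mean of 99% of usability problems to be identified (minimum of 97"%). It calls this size appropriate because "the product is in feasibility, and the intent is to assess the usability of the user interface to determine further design iterations".

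Three other places bear on the point:

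- Section 7.3 (Population): "Approximately 60-70 participants will be recruited for the trial by NTLSC".
- Section 7.2 (Objectives): the mask is to be evaluated "in a home environment in regards to the participants' view of overall comfort, experience and satisfaction".
- Sections 9.5 and 9.7: "Since the trial is to inform product development, no statistical design is required", and "There is no pass/fail criteria for this trial as the primary objective of the trial is to gain feedback".

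Section 8.12 (Number of Trial Subjects) is redacted. So are the hypothesis (7.1), the variables (8.5) and the detail of participant flow (8.10).

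**The concern.** No sample size finds a fixed share of problems whatever their frequency, yet section 9.6 attaches no condition to its percentages. It names no frequency, no detection model and no class of problems. A reader could infer that a clean run in 30 users leaves at most 1% to 3% of problems undiscovered. For less common problems that inference would be badly wrong.

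Two further features add to the unease. The figure concerns finding problems, whereas the primary objective concerns how participants rate comfort, experience and satisfaction, and section 9.6 gives no precision for those ratings. Also, the number justified (30) is about half the number to be recruited (60 to 70), and the visible text does not connect the two. Section 9.6 is the only visible statistical justification for the study's size, so an overstatement there would matter if a decision rested on it.

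**Working it through.** **Inputs.** From section 9.6: n = 30 as a minimum, mean share found 99%, minimum share 97%. From section 7.3: 60 to 70 recruited. The documents give no problem frequency p.

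**Can the plan's figure be reproduced?** No. Without p, or the data behind the cited guidance, 99% and 97% cannot be derived from the documents. One can only ask which p they would imply under an assumed model.

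**Step 1: one common frequency.** Assume independent users and the same p for every problem. The chance of seeing a problem at least once is 1 − (1 − p)^n. Solving for p at detection level c gives p = 1 − (1 − c)^(1/n).

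- n = 30, c = 97%: 1 − 0.03^(1/30) = 0.110
- n = 30, c = 99%: 1 − 0.01^(1/30) = 0.142
- n = 30, c = 95%: 1 − 0.05^(1/30) = 0.095

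Detection by frequency:

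| p | n = 30 | n = 60 | n = 70 |
|---|---|---|---|
| 10% | 95.8% | 99.8% | 99.9% |
| 5% | 78.5% | 95.4% | 97.2% |
| 2% | 45.5% | 70.2% | 75.7% |
| 1% | 26.0% | 45.3% | 50.5% |

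At n = 30, a problem affecting 1 user in 20 is therefore missed 21.5% of the time (100 − 78.5), and one affecting 1 in 50 is missed 54.5% of the time (100 − 45.5).

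**Step 2: does this contradict 99%/97%?** Section 9.6 reports a mean and a minimum share of problems found. Step 1 gives a detection probability for a single problem. The two coincide only if all problems share one p, which the plan does not say.

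Let p vary between problems as Beta(a, b), an assumption. The mean share found at n = 30 is 1 − B(a, b + 30)/B(a, b), where B is the beta function. For a = 1 this is 1 − b/(b + 30). Setting it to 99% gives b = 0.303, and the share of problems with p below 0.11 is 1 − 0.89^0.303 = 3.5%. For a = 2, 3, 5 and 10, solved the same way, the shares are 5.8%, 7.3%, 8.5% and 8.2%. A 99% mean share is thus compatible with some problems rarer than 11%.

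Other assumptions give less favourable answers. With Beta(1, 9), whose mean is 10% and whose mass sits near zero, the mean share at n = 30 is 1 − 9/39 = 76.9%. The result turns on the assumed distribution, and the documents do not settle it.

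**Step 3: 30 against 60 to 70.** Thirty is a minimum for each investigation, and recruiting 60 to 70 satisfies it. If everyone counts towards one investigation, the 97% and 99% thresholds from Step 1 fall to 5.7% and 7.4% (n = 60) or 4.9% and 6.4% (n = 70). Whether recruits are split across investigations cannot be seen.

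**Step 4: precision of the ratings.** Suppose, as an assumption, that comfort were a yes/no rating with 80% favourable. Exact 95% intervals would be 61.4% to 92.3% for 24 of 30, and 68.2% to 88.9% for 52 of 65. No visible text defines such a proportion. Section 8.4.1 refers to custom questionnaires, interviews and device data.

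**The case for a change.** The strongest case for a change is that it is cheap and makes the text more honest. One sentence could say that 30 participants give a 95% chance of seeing any problem affecting at least 9.5% of users. If 60 to 70 all count towards one investigation, that threshold falls to 4.9% to 4.2% (1 − 0.05^(1/60) and 1 − 0.05^(1/70)). The findings feed design iterations, and a team that took the 97% minimum at face value might regard discovery as nearly complete. A share observed for one product and set of tasks need not carry over to a mask worn at home. In a single-arm study, moreover, estimates and their uncertainty are the main output.

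Part of this stands. The assumption is missing, the binomial arithmetic is right, and rarer problems will often go unseen in 30 users.

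The rest does not carry the point. The cited guidance is not available here, so nothing shows that it is misreported or wrong for the conditions it describes. The plan does not claim that the percentages hold at every frequency. Interval widths for comfort would first need a responder definition, which is more than a wording change. Finally, no visible rule treats a clean run as proof that no problems remain.

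**Conclusion.** The concern identifies a missing detail that leads to no change. Section 9.6 quotes a share of problems found without the frequency assumption behind it. Under one common frequency, the quoted levels correspond to problems affecting about 11% to 14% of users at n = 30. That does not refute a mean and minimum share when frequencies differ between problems, and recruiting 60 to 70 does not conflict with a floor of 30.

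What decides the matter is what the figure is used for. The plan disclaims a statistical design and sets no pass/fail criterion, and section 9.8 rules out an interim analysis. Feedback would be collected from the same people and used in the same way with or without the extra sentence. An analyst writing the report can say that rarer problems may have been missed.

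This rests on the visible text. It assumes that the redacted sections, notably 7.1, 8.5 and 8.12, contain no decision that depends on the 99% or 97% figure. Sections 9.5 and 9.7 point that way.

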9.7. Pass/Fail Criteria

There is no pass/fail criteria for this trial as the primary objective of the trial is to gain feedback.

[REDACTED]	[REDACTED]
[REDACTED]	[REDACTED]

9.8. Statistical Termination

No interim analysis will be conducted as statistical outcomes will not change the conduct of the study.

9.9. Statistical Procedure Deviations

Statistical procedure deviations will be reported to the principal investigator and the sponsor. Deviations from the original statistical plan will be explained in the final study report.

9.10. Selection Criteria

All participants who consent, and are fitted with a mask that they attempt to sleep on will be included in the analysis. Please see section 8.10 for information on participant flow throughout the trial.

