8.4. End Points

8.4.1. Primary Outcomes

- The F&P mask is comfortable to use for the participant as measured by the custom questionnaires and recorded during the interviews.
- The mask is easy to use, accepted by the participant and provides adequate treatment for OSA during in-home use, measured via participant feedback and PAP data download (if applicable)
- The acceptability of the mask [REDACTED] through interview feedback/ participant questionnaire .

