8.9. Point of Enrolment

Participants will be recruited; who are prescribed either APAP, CPAP or Bi-level PAP for OSA at NTLSC. The principal investigator (or those identified in the delegation log) will ask the subjects whether they are interested to take part in the trial. The participants who meet the inclusion/exclusion criteria and provide informed consent and will then be enrolled in to the trial. [REDACTED]

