8.11. Withdrawal Criteria

Participants will be informed that they have the right to withdraw from the study at any time, without prejudice to their medical care, and are not obliged to state their reasons. The participants is informed that they can revert back to their usual therapy during the clinical investigation if they have reason to do so. Additionally the investigator may withdraw a participant at any time for the following reasons:

- Protocol Violation
- Safety concerns
- Serious illness
- Adverse event

[figure not shown]
The reason for participant discontinuation in the study is to be recorded in the CRF and source document.

[figure not shown]

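### On the readable text, the section 9.10 analysis set leaves out enrolled participants whom the mask itself kept from being fitted or from trying to sleep, so the usability-problem list may be incomplete and any acceptability summary too favourable

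*Combined protocol and SAP*

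**What the plan says.** Section 8.9 sets the point of enrolment: "The participants who meet the inclusion/exclusion criteria and provide informed consent and will then be enrolled in to the trial". Nothing readable there requires a fitting or a night of use, although the end of that section is redacted.

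Section 9.10 then defines who is analysed: "All participants who consent, and are fitted with a mask that they attempt to sleep on will be included in the analysis". It continues: "Please see section 8.10 for information on participant flow throughout the trial". Section 8.10 is redacted in the public copy.

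Section 8.4.1 lists the primary outcomes. One reads in part "The mask is easy to use, accepted by the participant and provides adequate treatment for OSA during in-home use". Another is the acceptability of the mask, assessed "through interview feedback/ participant questionnaire"; a redaction stands in the middle of that sentence.

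Section 9.6 gives the purpose of the sample: "the intent is to assess the usability of the user interface to determine further design iterations". Section 9.7 sets no pass/fail criterion because the trial exists to collect feedback, and section 9.5 sets no statistical design.

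On people who leave, section 8.11 says "The reason for participant discontinuation in the study is to be recorded in the CRF and source document", and also that participants "are not obliged to state their reasons".

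**The concern.** Both conditions that section 9.10 adds to consent come after enrolment, and both can fail because of the product under study. A mask that cannot be made to fit, or that a participant will not try to sleep in, is about the clearest negative result that a usability study can produce. Under the stated rule the person who supplies that result is not in the analysis.

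Two things are at stake. First, a problem that shows itself only as a failed fitting or a refusal to sleep in the mask cannot appear in a problem list drawn from the analysed set, however many people are recruited. Second, if an acceptability proportion is given, people who reject the mask at the outset are missing from the denominator, and the figure can only move in the favourable direction. No pass/fail decision is affected, since the plan has none.

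**Working it through.** **Step 1: the two rules side by side.**

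| Stage | Condition in the readable text | Can the mask make it fail? |
|---|---|---|
| Enrolment (8.9) | Eligible and consented | No |
| Analysis (9.10) | Consented | No |
| Analysis (9.10) | Fitted with a mask | Yes |
| Analysis (9.10) | Attempts to sleep on it | Yes |

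A participant can therefore be enrolled and not meet 9.10. One who tries to sleep and then stops does meet it, so the gap is confined to those never fitted and those who never made an attempt.

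**Step 2: which outcomes are touched.** Leak, PAP data and in-home comfort need some use of the mask, so the current set suits them. The ease-of-use outcome in 8.4.1 is worded for in-home use, so the current set suits that too. The usability-problem list (9.6) and acceptability (8.4.1) are different: a failed fitting or a refusal is itself an observation on both, subject to whatever the redacted words in the acceptability outcome say.

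**Step 3: the plan's own figure.** Section 9.6 states that 30 participants identify a mean of 99% of usability problems, with a minimum of 97%. It takes this from a cited guidance and gives no per-participant detection probability, so the figure cannot be reproduced from the documents. As a consistency check, take the simple model in which the share found is 1 − (1 − d)^n, where d is the chance that one participant reveals a problem. At n = 30, a share of 97% needs d = 1 − 0.03^(1/30) = 0.110, and 99% needs d = 1 − 0.01^(1/30) = 0.142. Nothing is contradicted. But for a problem that appears only among people outside the analysed set, d within that set is 0 and the share found is 0 at any n.

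**Step 4: effect on a proportion, if one is reported.** Inputs: N is the corrected denominator, k the number of omitted mask-related non-users, and p the favourable share among the N − k in the current set. N is taken as 60 to 70 (section 7.3, assuming a fitting is attempted for every recruit) or 30 (the minimum in section 9.6). The documents do not give k or p.

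- Proportion in the current set: p.
- Proportion with the k counted as failures: p(N − k)/N.
- Shift: p − p(N − k)/N = p·k/N, which is at most k/N.

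For k = 1 the most it can be is:

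- N = 60: 1/60 = 1.7 percentage points
- N = 70: 1/70 = 1.4 percentage points
- N = 30: 1/30 = 3.3 percentage points

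For k = 0 the shift is zero.

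**Step 5: illustration with assumed counts, not an estimate.** Take N = 60 and a favourable share near 80% in the current set.

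| k omitted | Current set | With omitted counted | Shift (points) |
|---|---|---|---|
| 3 | 46/57 = 80.7% | 46/60 = 76.7% | 4.0 |
| 6 | 43/54 = 79.6% | 43/60 = 71.7% | 8.0 |
| 12 | 38/48 = 79.2% | 38/60 = 63.3% | 15.8 |

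The spread shows that the result depends almost wholly on k.

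**The case against.** The strongest objection is redaction. Section 9.10 sends the reader to section 8.10 for participant flow, and what happens between consent, fitting and the first night is exactly that. Section 8.10 cannot be read, nor can the two questionnaires listed in the contents, the end of 8.9, or the middle of the acceptability outcome, where a limiting phrase could stand. This stands in full: a reader might infer that the plan ignores fitting failures, and the documents do not support that. They show only that the readable rule does not cover them.

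Second, 9.10 says who is included and does not say that nobody else may be. That is true, and nothing bars listing other feedback. But the treatment of non-qualifiers is then left to be settled after the data are seen.

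Third, the trial concerns use at home. A reader might infer that every failed fitting should be scored as a failure of ease of use as well. The wording of 8.4.1 does not support this: someone never fitted has no in-home use to rate, and scoring them would alter the outcome. The current set should stay for that outcome.

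Fourth, 1/N might be read as a limit on the total bias. It is the effect of one omitted person, and k is not bounded by anything in the documents. No readable text says that a proportion will be reported at all.

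Fifth, discontinuation reasons already go into the CRF, so the sponsor may learn of these cases anyway. That is so, but no readable text carries those reasons into the analysis, and participants need not give one. A reader might also want cases of unknown cause scored both as failures and as unrelated. In a feasibility study without a statistical design that is more than the readable text calls for; a separate count of unknowns is enough.

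**Conclusion.** The point holds in a limited form. The readable analysis rule conditions on two events that the mask can prevent, so mask-related non-fitting and refusal to sleep in the mask fall outside it. The consequence is a possibly incomplete list of usability problems and a possibly over-favourable acceptability summary. No test, error rate or go/no-go decision is affected.

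The size is unknown and may be zero. Excluding people intolerant to PAP (section 8.8) may keep the number small, but the documents give no count. The per-person figures in step 4 assume that a proportion is reported and that N is the number of people in the corrected denominator. Confidence is medium, because the redacted text may already settle the matter. This is a cheap improvement to the plan and does not undermine the trial.

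**What to change.** Amend section 9.10 as follows.

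1. Keep the current set for in-home comfort, in-home ease of use, leak and PAP data.
2. For the list of usability problems and the acceptability summary, also include consented participants for whom a fitting was attempted. Report mask-related non-fitting, or mask-related refusal to sleep in the mask, as usability/acceptability failures, and count them in the denominator if an acceptability proportion is given.
3. For all consented participants outside the current set, report counts and the reasons recorded in the CRF, grouped as mask-related, unrelated and unknown.
4. If section 8.10 already does this, say so in 9.10.

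The cost is about a paragraph and one short table, built on reasons that section 8.11 already requires to be recorded. No extra participants or visits are needed. The downsides are a possibly less favourable figure, a judgement on cause for each non-user, and some reasons that will stay unknown.

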9.11. Statistical Data Management

Fisher and Paykel Healthcare may consult an external statistician to assist with the analysis of the data.

10. Adverse Events and Termination

[figure not shown]
[figure not shown]
An Adverse Event (AE) is any adverse change from the participant's baseline condition, i.e., any unfavorable and unintended sign or symptom or disease that occurs during the course of the study, whether or not considered related to the PAP treatment. All clinically significant AEs occurring during the study that were not present prior to the commencement of PAP treatment, will be recorded in the CRF and source document and followed by the Investigator until resolution or stabilization occurs in accordance with GCP.

Serious AE's are considered to be AE's that result in any of the following outcomes, regardless of their relationship to the PAP treatment:

- Death
- A life-threatening AE
- In-patient hospitalization or prolongation of existing hospitalization
- A persistent or significant disability/incapacity
- A congenital abnormality/birth defect

[REDACTED]	[REDACTED]
[REDACTED]	[REDACTED]
[REDACTED]	[REDACTED]

10.3. Reporting Adverse Events

Any serious AE, due to any cause, that occurs during the study period, must be reported immediately (within the next business day) by telephone to the sponsor. In addition to the initial telephone report, a Serious Adverse Event form must be completed and sent via facsimile to the sponsor. All serious AE's must also be recorded on the AE page of the CRF. Additionally, all serious AE's must be reported to the Independent Review Board (IRB) as per the IRB's requirements.

[REDACTED]	[REDACTED]
[REDACTED]	[REDACTED]
[REDACTED]	[REDACTED]

10.4. Early Termination

The study may be discontinued at any time on the advice of the responsible investigator on the basis of new information regarding safety or efficacy. Additionally, the study may be terminated if progress is unsatisfactory. The following documentation is required if the appropriate party terminates a clinical trial.

10.5. Investigator

If the investigator terminates or suspends a trial without prior agreement of the sponsor, the investigator should inform the institution, where required by the applicable regulatory requirements and the investigator/institution should promptly inform the sponsor and the IRB, and should provide the sponsor and the IRB a detailed written explanation of the termination or suspension.

10.6. Sponsor

If the sponsor terminates or suspends a trial, the investigator should promptly inform the institution, where required by the applicable regulatory requirements, and the investigator/institution should promptly inform the IRB and provide the IRB a detailed written explanation of the termination or suspension.

